8.2.7.10 SAFETY SERUM RETENTION SAMPLE

Safety serum retention samples will be collected on Day 0 (prior to malaria challenge) and at EOS. Participants consent to the mandatory storage of these samples and their use for retrospective safety assessments if required. Samples will be stored indefinitely at QIMR Berghofer.

8.2.7.11 COVID-19 TESTING

A COVID-19 PCR test will be performed at the eligibility visit (Day -3 to Day -1) and a rapid antigen test (RAT) will be performed immediately prior to scheduled malaria inoculation (Day 0). Any participant testing positive will be ineligible for enrolment in the study.

An additional PCR test will be performed after malaria inoculation on Day 6, and an additional RAT will be performed upon admission to the clinical trial unit on Day 7 PM. Any participant testing positive will be administered definitive antimalarial medication and will be withdrawn from the study without being administered the IMP. If the participant tests positive while in clinic (i.e. the RAT on Day 7 PM), the first dose of definitive antimalarial medication will be administered at the clinic while remaining doses will be taken by the participant at home. If the result of the PCR test on Day 6 comes back positive, definitive antimalarial treatment will be delivered to the participants' home address, and a phone call will be made to ensure that the first dose is taken.

Participants will be contacted daily via phone to ensure treatment compliance for the remaining doses and to ascertain any adverse events. Where possible, an early termination visit (Section 12.1) will be conducted a minimum of 7 days following the positive COVID-19 test when the Investigator deems the risk of transmission is low.

Additional COVID-19 testing may be performed after IMP dosing at the discretion of the Investigator. If a participant tests positive during the confinement period (Day 7 PM to Day 11), definitive antimalarial treatment will be initiated and the participant will be sent home and followed-up via phone to ensure all doses are taken and ascertain any adverse events. Daily RATs will be performed for all remaining participants.

If a participant tests positive to COVID-19 during the outpatient follow-up period (Day 12 to Day 27), definitive antimalarial treatment will be initiated (either in clinic or delivered to the participants' home address as specified above).

Where possible, participants testing positive to COVID-19 after IMP dosing will resume study visits a minimum of 7 days after the date of the positive test.

Clinical management of participants with COVID-19 will follow Queensland Health Guidelines. If a participant's condition was to deteriorate while isolating at home, the participant will be assessed over the phone by the Investigator and may be advised to present to a hospital Emergency Department if required, or clinical site staff may call 000 if appropriate. In the event that a participant is admitted to hospital, the Principal Investigator will continue to liaise with treating clinicians.

8.2.7.12 PARASITE EX VIVO VIABILITY

Determining parasite growth in *ex vivo* cultures is an exploratory objective of this study. *Ex vivo* growth is a measure of parasite viability. While 18S qPCR quantifies all parasites (including those non-viable or dead in circulation), only viable parasites are able to replicate in *ex vivo* culture. Modelling of parasite growth observed *ex vivo* enables the fraction of viable parasites present in blood samples to be determined. The results of parasite *ex vivo* growth analyses will be supportive to malaria 18S qPCR data in determining the kinetics of parasite clearance following MMV367 dosing (secondary endpoint). Short term *ex vivo* cultures will be established from blood samples collected pre-MMV367 administration (Day 8), then at several time-points post-MMV367 administration.

8.2.7.13 PARASITE DRUG RESISTANCE

Blood samples will be collected from participants experiencing parasite regrowth to investigate if parasites have acquired resistance to MMV367 (exploratory objective). Parasites will be genotyped and *in vitro* drug sensitivity testing will be performed.

8.3 ADVERSE EVENTS AND SERIOUS ADVERSE EVENTS

8.3.1 DEFINITION OF ADVERSE EVENTS (AE)

An AE is any untoward medical occurrence, i.e., unfavourable and unintended sign (including an abnormal laboratory finding), symptom or disease that occurs in a participant during the course of the trial. An AE does not necessarily have a causal relationship with trial treatments or procedures.

AEs include, but are not limited to:

- A new symptom, sign or medical condition.
- A disease or medical condition detected or diagnosed during the course of the trial even though it may have been present prior to the start of the trial.
- An exacerbation of a pre-existing medical condition/disease.
- An increase in frequency or intensity of a pre-existing episodic disease or medical condition.
- Continuous persistent disease or symptoms present at trial start that worsen following the start of the trial.
- An abnormal assessment (e.g., change on physical examination, ECG finding) if it represents a clinically significant finding that was not present at trial start or worsened during the course of the trial.
- An abnormal laboratory test result if it represents a clinically significant finding (e.g., CTCAE grade 2 or above), symptomatic or not, which was not present at trial start or worsened during the course of the trial or led to dose reduction, interruption or permanent discontinuation of trial treatment.

Borderline abnormal laboratory findings and other objective assessments should NOT be routinely captured and reported as AEs. However, abnormal laboratory findings or other objective measurements that meet the following criteria should be captured and reported in the AE section of the eCRF:

- The result meets the criteria for reporting as an SAE.
- The test result is associated with accompanying symptoms, and/or
- It requires additional diagnostic testing or medical/surgical intervention, and/or
- It leads to a change in trial dosing, or discontinuation from the trial, significant additional concomitant drug treatment, or other therapy, and/or
- It is considered by the Investigator to be clinically significant or represent a clinically significant change from baseline.

Merely repeating an abnormal test, in the absence of any of the above conditions, does not constitute an AE. Any abnormal test result that is determined to be an error does not require reporting as an AE. Surgical procedures themselves are not AEs; they are therapeutic measures for conditions that may, or may not, be AEs. Malaria in itself is not considered an AE.

8.3.2 DEFINITION OF SERIOUS ADVERSE EVENTS (SAE)

An SAE is defined as an event that fulfils at least one of the following criteria:

- Results in death.
- Is life-threatening
 - The term "life-threatening" in the definition of "serious" refers to an event in which the participant was at immediate risk of death at the time of the event; it does not refer to an event which hypothetically might have caused death if it was more severe.
- Requires inpatient hospitalisation or prolongs existing hospitalisation, unless this is for:
 - Elective or pre-planned treatment for a pre-existing condition that is unrelated to the trial and has not worsened since the start of the trial.
 - Cosmetic surgery, or for social reasons, or respite care in the absence of any deterioration in the participant's general condition.
- Results in persistent or significant disability/incapacity.
- Is a congenital abnormality/birth defect.
- Is considered medically important
 - Medical and scientific judgement should be exercised in deciding whether other AEs are to be considered serious, such as important medical events that may not be immediately life-threatening but may jeopardise the participant or may require intervention to prevent one of the other outcomes listed in the definition above. Examples of such events are: intensive treatment in an emergency room or at home for allergic bronchospasm; blood dyscrasias; convulsions that do not result in hospitalisation; development of drug dependency or drug abuse.

A Suspected Unexpected Serious Adverse Reaction (SUSAR) is any SAE where a causal relationship with a trial intervention (malaria challenge agent, MMV367, definitive antimalarial medication) is at least a reasonable possibility, and the event is not listed in the reference safety information (IB or Australian Prescribing Information for the definitive antimalarial medication).

8.3.3 ADVERSE EVENTS OF SPECIAL INTEREST (AESI)

An AE of special interest (AESI), whether serious or non-serious, is one of scientific and medical concern specific to the Sponsor's product or program, for which ongoing monitoring and rapid communication by the Investigator to the Sponsor and medical monitor could be appropriate. Such an event might require further investigation in order to characterise and understand it. Depending on the nature of the event, rapid communication by the trial Sponsor to other parties (e.g., regulators) might also be warranted (CIOMS VI, ICH E2F, 2010). Any abnormalities listed below should be reported as an AESI.

Hepatic:

- ALT or AST $> 5 \times$ ULN
- ALP $> 2 \times$ ULN (in the absence of known bone pathology)
- Total bilirubin $> 2 \times$ ULN (in the absence of known Gilbert syndrome)
- Any AST or ALT value $> 2 \times$ ULN and total bilirubin $> 1.5 \times$ ULN
- Any ALT or AST value $> 2 \times$ ULN and INR > 1.5
- Potential Hy's Law cases (defined as ALT or AST $> 3 \times$ ULN and total bilirubin $> 2 \times$ ULN [mainly conjugated fraction] without notable increase in ALP to $> 2 \times$ ULN)
- Any clinical event of jaundice (or equivalent term)
- ALT or AST $> 2 \times$ ULN accompanied by (general) malaise, fatigue, abdominal pain, nausea, or vomiting, or rash with eosinophilia (eosinophil percent or count above the ULN).

Cardiac:

- QTcF at any time > 480 msec
- Bundle branch block (except right bundle branch block that was present prior to MMV367 administration)
- Any arrhythmia, except:
 - sinus bradycardia that is clinically asymptomatic and not associated with any other relevant ECG abnormalities
 - sinus tachycardia that is clinically asymptomatic, is associated with a body temperature $> 38.0^{\circ}\text{C}$, and not associated with any other relevant ECG abnormalities
 - respiratory sinus arrhythmia
 - wandering atrial pacemaker, or
 - isolated single premature atrial/ventricular complex (i.e., no bigeminy, trigeminy, couplets, triplets or salvos) that does not occur more than once in a particular ECG tracing.

Haematological:

- Haemoglobin drop > 20.0 g/L from baseline (at eligibility visit)
- Absolute neutrophil count (ANC) $< 0.5 \times 10^9/\text{L}$.
- Platelet count $< 75 \times 10^9/\text{L}$.

Dermatological: *†

Clinical signs of possible cutaneous adverse reactions such as:

- Dermatitis
- Rash including
 - erythematous
 - macular
 - papular
 - maculopapular
 - pruritic
 - pustular
 - vesicular

*If one of these cutaneous reactions is observed, pictures of the lesions should be obtained when feasible.

†Dermatological AEs need not be reported as AESIs if clearly unrelated to the malaria challenge agent or IMP (e.g. rash from cannula dressing or ECG dots).

All AESIs, including those that do not meet the definition of an SAE, must be reported as per section 8.3.7.

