4 STUDY DESIGN

4.1 OVERALL DESIGN

This is an open-label, adaptive study that will utilise the *P. falciparum* induced blood stage malaria (IBSM) model to characterise the pharmacokinetic/pharmacodynamic (PK/PD) profile and safety of MMV367 (the IMP). Up to 18 participants will be enrolled in cohorts of up to 6 participants each. The study will proceed as follows for all participants:

- Screening period of up to 28 days to recruit healthy adult volunteers.
- Day 0: Intravenous inoculation with approximately 2,800 viable *P. falciparum*-infected erythrocytes.
- Days 1-3: Daily follow up via phone call or text message.
- Days 4-7: Daily site visits for clinical evaluation and blood sampling to monitor malaria parasitaemia via quantitative polymerase chain reaction (qPCR).
- Day 7 PM: Start of confinement within the clinical trial unit.
- Day 8: Administration of a single oral dose of the IMP (MMV367). Different doses of MMV367 will be administered across and within cohorts in order to effectively characterise the PK/PD relationship (see Section 4.3 for dose selection rationale).
- Days 8-11: Regular clinical evaluation and blood sampling to monitor malaria parasitaemia and measure MMV367 plasma concentration.
- Day 11 AM: End of confinement within clinical trial unit.
- Days 12-23: Outpatient follow-up for clinical evaluation and blood sampling.
- Day 24: Initiation of compulsory definitive antimalarial treatment with Riamet® (artemether/lumefantrine) and/or other registered antimalarials if required (see section 6.1). Treatment will be initiated earlier than Day 24 in the event of:
 - Insufficient parasite clearance following IMP dosing (parasitaemia not reduced ≥ 10 -fold by Day 10 compared with peak parasitaemia on Day 8).
 - Parasite regrowth following IMP dosing (initial parasite clearance is followed by asexual parasite regrowth above 5000 parasites/mL).
 - Participant discontinuation/withdrawal (see Section 7),
 - Investigator's discretion in the interest of participant safety.
- Day 27: End of study visit for final clinical evaluation and to ensure complete clearance of malaria parasitaemia (at least one negative malaria PCR result required).

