4.2 SCIENTIFIC RATIONALE FOR STUDY DESIGN

The study design of this trial using the IBSM model has been used previously to safely and effectively determine the PK/PD relationship of several antimalarial agents [2-5,11]. The *P. falciparum* 3D7 challenge agent to be used to initiate blood-stage malaria infection in this study has been well characterised, with consistent and reproducible parasite growth occurring following intravenous inoculation of healthy participants in previous studies. Experience from these studies indicates that parasitaemia will be above

5,000 parasites/mL on Day 8 following inoculation, but clinical symptoms of malaria will either be absent or only mild to moderate in severity.

The duration of confinement within the clinic following dosing with MMV367 on Day 8 (72 hours) is considered appropriate to ensure close monitoring of participants for safety purposes and to enable frequent blood sampling for parasitaemia and drug concentration measurements. Blood sampling time points have been selected with consideration of human PK data from the FIH study of MMV367, as well as preclinical data on the antimalarial activity of MMV367. These time points may be adjusted during the study, based on the emerging data in order to optimally determine the exposure/response relationship of MMV367.

The follow-up period from MMV367 dosing on Day 8 to initiation of compulsory definitive antimalarial treatment on Day 24 (16 days) is equal to approximately 22 times the elimination half-life of MMV367 (approximately 17 hours). This duration was selected to allow sufficient time for parasite regrowth, which is required to define the PK/PD relationship of MMV367. Further, this duration will ensure that participants have a negligible blood concentration of the IMP at the completion of the study on Day 27.

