8.3.6 ADVERSE EVENT REPORTING

It is the Investigator's responsibility to document and report all AEs occurring in the clinical trial whether spontaneously reported by the participant, observed by the Investigator (either directly or by laboratory or other assessments), or elicited by general questioning. The period of observation for collection of AEs extends from the time of inoculation with the malaria challenge agent to EOS. These AEs must be recorded on specific AE pages of the eCRF. Events reported prior to this will be recorded as medical history, unless the symptoms worsen during the trial.

The following information should be recorded for all AEs:

- Description
- Dates and times of onset and resolution
- Seriousness (SAE or not)
- AESI (yes/no)
- Severity
 - If severity of an AE changes, only one AE will be reported, with the highest severity recorded in the eCRF and listings and tables. In the clinical file (source data), the description of the AE will report the various severities observed over time.
 - If the AE resolves and then reoccurs, then two AEs will be reported.
- Action taken in response to the AE (including treatment given).
- Outcome.
- Relationship to the trial treatments or procedures (causality assessment), including the IMP, malaria challenge agent, definitive antimalarial medications, or any other treatment or procedure conducted during the trial.

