#### 11.3.1.2.2. Tables

The number of events, as well as the number and percentage of participants experiencing an AE, will be summarised by, dose group and overall as follows:

Overall summary of IEAEs (FA set)  
Overall summary of TEAEs (IMP set)

Summary of IEAEs by System Organ Class and Preferred Term - All Causalities (FA set)  
Summary of TEAEs by System Organ Class and Preferred Term - All Causalities (IMP set)

Summary of IEAEs by System Organ Class, Preferred Term and Maximum Severity - All Causalities (FA set)

Summary of TEAEs by System Organ Class, Preferred Term and Maximum Severity - All Causalities (IMP set)

Summary of Malaria-Related IEAEs by System Organ Class and Preferred Term (FA set)  
Summary of IMP-Related TEAEs by System Organ Class and Preferred Term (IMP set)

Summary of Malaria-Related IEAEs by System Organ Class, Preferred Term and Maximum Severity (FA set)

Summary of IMP-Related TEAEs by System Organ Class, Preferred Term and Maximum Severity (IMP set)

Summary of IE SAEs by System Organ Class and Preferred Term - All Causalities (FA set)  
Summary of TE SAEs by System Organ Class and Preferred Term - All Causalities (IMP set)

Overall Summary of IE AESIs (FA set)  
Overall Summary of TE AESIs (IMP set)

Summary of IE AESIs by System Organ Class and Preferred Term - All Causalities (FA set)  
Summary of TE AESIs by System Organ Class and Preferred Term - All Causalities (IMP set)

Summary of IEAEs Leading to Study Discontinuation by System Organ Class and Preferred Term - All Causalities (FA set)

Summary of TEAEs Leading to Study Discontinuation by System Organ Class and Preferred Term - All Causalities (IMP set)

For the summary tables, participants who experience the same AE (in terms of the MedDRA preferred term) more than once will only be counted once.

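### A new right bundle branch block arising between inoculation (Day 0) and MMV367 dosing (Day 8) is exempt from special-interest reporting, although inoculum-emergent AESIs are counted from inoculation

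*Protocol*

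**What the plan says.** Protocol 8.3.3 (Cardiac) and SAP 11.3.1 (Cardiac) carry the same criterion: "Bundle branch block (except right bundle branch block that was present prior to MMV367 administration". The list is introduced by "Any abnormalities listed below should be reported as an AESI", with no restriction to events thought to be caused by MMV367.

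The timing comes from protocol 4.1: "Day 0: Intravenous inoculation with approximately 2,800 viable" infected erythrocytes, then "Day 8: Administration of a single oral dose of the IMP (MMV367". Protocol 8.3.6 sets the AE window: "The period of observation for collection of AEs extends from the time of inoculation with the malaria challenge agent to EOS". SAP 11.3.1 defines inoculum-emergent events as those starting at or after inoculation, and says AESIs are evaluated as inoculum- or treatment-emergent. SAP 11.3.1.2.2 plans the matching table: "Overall Summary of IE AESIs (FA set").

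The haematological part of the same list has a pre-inoculation reference: "Haemoglobin drop > 20.0 g/L from baseline (at eligibility visit").

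**The concern.** The exception evidently exists so that a right bundle branch block a participant brings into the trial is not reported as new. Tied to Day 8, it also covers a block that was absent before inoculation and appeared while the infection was growing and no drug had been given.

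Safety of the blood-stage infection is a secondary objective in protocol section 3, and protocol 2.2.1 names ECG monitoring among its precautions against cardiac events. The Day 8 pre-dose ECG is the only scheduled ECG between inoculation and MMV367, so it is the one that best separates an effect of infection from an effect of the drug. For this one finding, the rule removes that ECG from AESI status, from the automatic 24-hour notification in protocol 8.3.7, and from the inoculum-emergent AESI tables on the FAS.

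**Working it through.** This is a check of definitions. The only arithmetic is a count of days and scheduled ECGs.

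**1. Type of block by time of onset** (protocol 8.3.3; SAP 11.3.1 is identical)

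| Onset | Left block, current text | Right block, current text | Right block, exception tied to pre-inoculation ECG |
|---|---|---|---|
| Before inoculation | not exempt | exempt | exempt |
| Day 0 to Day 8 pre-dose | AESI | **exempt** | **AESI** |
| After MMV367 | AESI | AESI | AESI |

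One cell changes. Pre-existing right block stays exempt under either anchor.

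**2. Days**

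Protocol 4.2 gives its own figure: "The follow-up period from MMV367 dosing on Day 8 to initiation of compulsory definitive antimalarial treatment on Day 24 (16 days"). This reproduces: 24 − 8 = 16.

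- Inoculation to dosing: 8 − 0 = 8 days.
- Share of the time to scheduled definitive treatment: 8 / 24 = one third. The other 16 days are covered for right block, and all 24 for left block.
- Share of the AE window to the Day 27 end-of-study visit: 8 / 27, about 30%.

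**3. Scheduled ECGs after inoculation** (protocol 1.3 and 12.1)

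These are Day 8 pre-dose, 24 h, 48 h, 72 h and end of study, five in all. Only the Day 8 pre-dose ECG falls in the exempt window. Unscheduled ECGs before dosing, which protocol 8.2 allows, would also fall in it. A block first seen there that persists stays exempt at the four later ECGs.

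**4. Is the list meant to cover the challenge agent?**

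- The dermatological footnote in 8.3.3 waives AESI reporting only for events clearly unrelated to the challenge agent or the IMP. It names both.
- The haemoglobin criterion is measured from the eligibility visit, before inoculation.
- SAP 11.3.1 and 11.3.1.2.2 evaluate and tabulate inoculum-emergent AESIs on the FAS.

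The right-block exception is out of step with all three.

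**5. Is a pre-inoculation reference available?**

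Yes. Protocol 8.2.5 takes triplicate ECGs at screening and on Day 0 before inoculation. Inclusion criterion 8 requires normal ECG parameters at both but lets the investigator accept a tracing abnormality judged not clinically relevant. A pre-existing right block is therefore possible, and the exception has a purpose that these ECGs can serve.

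**6. Would other ECG outputs show the change?**

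Only in part. SAP 11.3.7 reports ECG change from treatment baseline, although protocol 9.4.4 asks for change from each baseline. The Day 8 pre-dose ECG is then itself the baseline, and the Day 0 to Day 8 shift does not appear as a change. Observed values by visit, flags for QRS outside 50–120 msec, and the planned ECG Clinical Assessment table remain.

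**The case against.** The strongest defence is that the MMV367 anchor is deliberate. Protocol 8.3.3 describes AESIs as matters of concern to the sponsor's product or programme, and first exposure to the product is a coherent reference point for a pre-existing finding. The haemoglobin baseline might simply be a different choice for a different parameter. This does not carry the point, because the list, its dermatological footnote and the SAP tables treat the challenge agent as within scope.

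Other safeguards do stand, and they limit what is lost:

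- Protocol 8.2.5 and 8.3.1 make a clinically significant ECG finding that was not present at trial start an AE, and it would enter the inoculum-emergent AE tables.
- A medically important event is an SAE under 8.3.2 and receives the same 24-hour notification.
- Protocol 12.1.5 requires the Day 8 ECG to be obtained and reviewed before dosing, and 7.1 lists ECG signals among the grounds for not giving MMV367.

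The risk evidence is also modest. Protocol 2.2.1 reports four cardiac SAEs, but in sporozoite challenge studies. It states that none has been attributed to the challenge agents in studies of the present model, where the reported events were ventricular extra-systoles in two participants. Those belong under the separate arrhythmia bullet, which has no MMV367 anchor. No bundle branch block is reported.

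A reader might infer that any block developing during the infection can never be an AESI. The documents do not support that. Left block is an AESI whenever it occurs. Right block arising after MMV367 is an AESI too, even though the participant may remain infected until definitive treatment, as late as Day 24.

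A reader might also infer that cases are missed in participants who are inoculated but never dosed. The text does not settle this. One natural reading is that the exception cannot be met if MMV367 is never given, so the block is reported. That is an ambiguity, not a demonstrated loss.

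**Conclusion.** The point stands in narrow form. A new right bundle branch block with onset between inoculation and the Day 8 pre-dose ECG is exempt from AESI reporting and stays exempt afterwards. This conflicts with an AESI evaluation that starts at inoculation. What is lost is the AESI label, its table entry and the automatic 24-hour notice for a block that is not otherwise serious.

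Two assumptions apply. First, bundle branch block is governed by its own bullet; the text does not say whether the arrhythmia bullet also reaches a conduction block, and if it does, the gap closes. Second, a block first seen before dosing is read as present before dosing for the rest of the study. The documents give no rate from which to project a number of cases among up to 18 participants. Nothing here touches the primary PK/PD endpoint. Priority is low.

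**What to change.** In protocol 8.3.3 and SAP 11.3.1, change the exception so that it covers right bundle branch block present on the screening or Day 0 pre-inoculation ECG, in place of the reference to MMV367 administration. Change both documents together: the AESI flag is set when the event is recorded under protocol 8.3.6, so a SAP edit alone would not restore it.

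No separate classification rule is needed, because SAP 11.3.1 already makes any AE starting after inoculation inoculum-emergent. The change also gives never-dosed participants a defined reference.

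The cost is one phrase in each document, with no new ECG, visit or analysis, and at most a rare extra AESI report. Protocol 10.1.2 requires ethics committee approval for protocol changes, so it is sensible to include this in the next amendment.
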